6.4 Derived Variables

6.4.1 “Time To” variables

“Time to” variables such as time to follow-up, time to weight-bearing, and time to return to work will be computed in days as (date of interest - date of index procedure). “Time to” will be computed in weeks as (date of interest - date of index procedure)/7. “Time to” will be computed in months as (date of interest - date of index procedure)/30. “Time to” will be computed in years as (date of interest - date of index procedure)/365.25.

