## Schedule of Assessments

Study Activity	Visit 1	Visit 2	Visit 3	Visit 4	Visit 5	Visit 6	Visit 7	Visit 8	Visit 9	Study Exit
	Baseline 	Index Procedure	0-14 Day follow-up	14-21 Day follow-up (+3 days)	6 Week follow-up (±2 weeks)	4 Month follow-up (±2 weeks)	6 Month follow-up (±1 month)	12 Month follow-up (±1 month)	24 Month follow-up (±2 months)	
Informed Consent	X									
Demographics	X									
Medical and Surgical History	X	X								
Targeted Physical Exam	X									
Height / Weight 	X									
Blood Collection, if required 	X									
4-Point Monofilament Test, if required 	X									
Radiographic Imaging 	X				X	X	X	X	X	
VAS Pain Scale	X		X	X	X	X	X	X	X	
POSAS						X	X	X	X	
QOL Measurements 	X						X	X	X	
Medications Review	X	X	X	X	X	X	X	X	X	
Digital Photos of Foot	X	X	X	X	X	X	X	X	X	
Clinical Exam of Foot	X		X	X	X	X	X	X	X	
Foot Measurements	X	X	X	X	X	X	X	X		
Pregnancy Test (if applicable) 	X									
Inclusion/Exclusion Criteria	X 	X 								
Index Procedure		X								
Wound check/surgical site healing			X	X	X	X				
Return to Weight-Bearing Activities 			X	X	X	X	X			
Range of Motion 	X					X	X	X	X	
Secondary Surgical Interventions 			X	X	X	X	X	X	X	
Adverse Events Assessment 		X	X	X	X	X	X	X	X	
Radiographic Measurements 	X				X	X	X	X	X	
Health Economic Outcomes 			X	X	X	X	X	X	X	
General Satisfaction Questionnaire									X	
Study Exit										X

 Baseline visit study activities must occur within 90 days of the Index Procedure unless otherwise noted.

 BMI should be calculated from height and weight measurement to determine patient eligibility.

 Blood collection is required only if subject has diagnosis of diabetes to determine fasting plasma glucose levels or HbA1c.

 4-point monofilament test is required only if subject has diagnosis of diabetes or if warranted by PI to assess for peripheral neuropathy.

 Three radiographic views of the operative foot should be obtained per visit (weight-bearing AP, lateral and axial views of operative foot). The axial view should be collected using the study provided axial positioner.

 QOL assessment tools – MOxFQ and PROMIS-29 (PROMIS-25 for ages 14-17).

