**Index Procedure** – See **Section 7.2** for complete list of data collected during the Index Procedure. Concomitant procedures of the 1st ray should also be recorded. These include but are not limited to, akin osteotomy, bone graft harvest (synthetic or allogenic bone graft substitutes are not permitted), intercuneiform stabilization, traditional medial eminence resection, rongeur of the medial capsular ridge, and/or dorsal metatarsal bone resection. No concomitant procedures that alter the post-operative WB instructions are permitted (including evans and other calcaneal osteotomies, lesser TMT joint fusions, lisfranc or metatarsus adductus). Any complications during the procedure or deviations to the normal operative plans must also be recorded.

**POSAS:** See **Appendix 9**. The Patient and Observer Scar Assessment Scale will be collected per the Assessment instructions.

**Return to Weight-Bearing Activities** – The actual date that the subject was allowed to start to return to weight-bearing activities (protected WB in CAM boot, shoe and full unrestricted activities) should be recorded. The number of days from index procedure will be calculated by Clinindex. See **Section 5.3** for post-operative care and weight-bearing instructions.

**Secondary Surgical Interventions:** Any adverse event/complication that requires a subsequent secondary surgical intervention should be recorded. The reason for the subsequent surgical intervention and the action taken should be recorded. Subsequent secondary surgical interventions are defined as revisions, hardware removals, reoperations, supplemental fixations or other surgical intervention due to wound healing issues or infections at surgical site.

**Health Economic Outcomes:** The date the subject was allowed to return to work (or normal household activities if non-working), should be recorded while noting work status and work classification (sedentary, light work, medium work, heavy work, very heavy work). The date the subjects was allowed to return to full work (or full household activities if non-working), should be recorded while noting work status and work classification (sedentary, light work, medium work, heavy work, very heavy work – See **Appendix 1** for definitions). Any post-operative physical therapy requirements required for recovery of Lapiplasty® Procedure should be recorded. Any employment of home health services and the reason should be recorded.

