6.3 Missing Data

Effectiveness and health economic analyses will be based on available data, without imputation for missing values. For Quality of Life outcomes (MOxFQ and PROMIS-29/PROMIS-25), missing data will be handled as specified in the Derived Variables section. For safety analyses, missing event dates will be imputed as follows:

- If only month and year are reported, then day is assigned as the 15th of the month
- If only year is reported, then month and day is assigned as July 1st

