6.4.9 Non-union

Non-union is defined as pain at the TMT joint plus one or more of the following: lucency, hardware failure, or recurrence.

7 Statistical Analysis

All continuous variables will be summarized using the following descriptive statistics: n, mean, standard deviation, median, minimum, maximum, and where appropriate 95% confidence intervals (CIs). The frequency and percentages of observed levels will be reported for all categorical measures. In general, all summary tables will be annotated with the total population size relevant to that table, including any missing observations. Data listings will be sorted by site, subject, and when appropriate by visit type within subject.

Two-sided T-tests will be generated for change from baseline analyses. P-values ≥ 0.001 will be reported to 3 decimal places; p-values less than 0.001 will be reported as “ <0.001 ”. P-values less than 0.05 will be considered statistically significant. The mean, standard deviation, and any other statistics other than quantiles, will be reported to one decimal place greater than the original data. Quantiles, such as median, or minimum and maximum will use the same number of decimal places as the original data. Estimated parameters, not on the same scale as raw observations (e.g. regression coefficients) will be reported to 3 significant figures.

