7.2.2 Secondary Effectiveness Analysis

Effectiveness analyses will be performed on the following secondary endpoints:

- 1) Percentage of subjects with recurrence at 12 months where recurrence is defined as meeting 2 of the following 3 criteria: IMA of $\geq 12^\circ$, HVA $\geq 20^\circ$ and TSP ≥ 4 .

- 2) Percentage of subjects with recurrence at 12 months and 24 months where recurrence is defined as HVA >15°.
- 3) Percentage of subjects with recurrence at 12 months and 24 months where recurrence is defined as HVA >20°.
- 4) Percentage of subjects with successful correction at 6 weeks.
- 5) Change from baseline in radiographic angular/positional alignment for HVA, IMA, TSP, and sagittal plane at 6 weeks, 4 months, 6 months, 12 months, and 24 months.
- 6) Percentage of subjects with non-union (absence of clinical/radiographic healing) at 12 months.
- 7) Time to weight-bearing in a controlled ankle motion (CAM) boot, in days.
- 8) Time to weight-bearing in shoes, in weeks.
- 9) Time to return to full unrestricted activity, in months.
- 10) Change from baseline in pain at the base of the big toe (bunion related) assessed via VAS at 0-14 days, 14-21 days, 6 weeks, 4 months, 6 months, 12 months, and 24 months.
- 11) Change from baseline in Quality of Life at 6 months, 12 months, and 24 months as measured by PROMIS-29 (for adult subjects), PROMIS-25 (for pediatric subjects), and MOxFQ (for all subjects).
- 12) Change from baseline in range of motion of the 1st MTP dorsiflexion, plantarflexion, and dorsiflexion plus plantarflexion at 4 months, 6 months, 12 months, and 24 months.
- 13) Change from baseline in foot swelling measurements at 0-14 days, 14-21 days, 6 weeks, 4 months, 6 months, and 12 months.
- 14) Summary of POSAS responses over time at 4 months, 6 months, 12 months, and 24 months.

Statistical summaries will be produced in accordance with section 7, and listings will be generated by site, subject, and visit (where applicable) within subject.

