7.3.3 Return to Work

Time to return to work and time to return to full work (or normal household activities if non-working), in days, will be summarized.

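### Time to full unrestricted activity is summarised only in subjects with a date, and scheduled collection of that date stops at Visit 7, so the reported time is biased short

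*SAP*

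**What the plan says.** **Derivation and summary.** SAP 6.4.1 states: "time to weight-bearing, and time to return to work will be computed in days as (date of interest - date of index procedure"). SAP 6.3 adds: "Effectiveness and health economic analyses will be based on available data, without imputation for missing values". The general rule in SAP section 7 is: "All continuous variables will be summarized using the following descriptive statistics: n, mean, standard deviation, median, minimum, maximum", with confidence intervals where appropriate. SAP 7.2.2 item 9 lists "Time to return to full unrestricted activity, in months", and SAP 7.3.3 says: "Time to return to work and time to return to full work (or normal household activities if non-working), in days, will be summarized". Neither document names a censoring rule or a time-to-event estimate.

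**Collection.** In the Protocol's Schedule of Assessments the row "Return to Weight-Bearing Activities" is marked at Visits 3 to 7. Footnote 11 says this item holds the boot, shoe and full-activity information. It appears in the Visit 7 list (7.7) but not in the lists for Visit 8 (7.8) or Visit 9 (7.9). Visit 7 is at 6 months ± 1 month. The health economic item, which holds the work dates, runs from Visit 3 to Visit 9.

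**What the date is.** Protocol 7.12 asks for "The actual date that the subject was allowed to start to return to weight-bearing activities", covering boot, shoe and full activity. For work it says: "The date the subject was allowed to return to work (or normal household activities if non-working), should be recorded". The endpoints in SAP 1.2.2 (items 4 to 6) and 1.2.3 (items 2 and 3) are named as times to start or to return.

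**The concern.** A subject who has not been cleared has no date, and under an available-data rule that subject drops out. The loss depends on the outcome itself, because the slowest recoverers are the ones missing. Protocol 5.3 lets clinically stable subjects begin low-impact exercise at the 4-month visit, and the date of permission for running and jumping is recorded from that stage. This milestone therefore falls close to the last scheduled capture. Anyone cleared between Visit 7 and Visit 9 is seen again twice but is not asked.

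Early return is part of the study's purpose: early weight-bearing is in the title, and Protocol Appendix 5 lists fast return to normal activities as a possible benefit. A recovery time that is short because of its method would be read in that light.

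**Working it through.** The plan states no figure for these endpoints, so there is nothing to reproduce. The check has four parts.

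**1. Direction, without a distribution.** Suppose a share *p* has no date because those subjects were all cleared later than the dated ones. The median of the dated subjects is then the true (1 − *p*)/2 quantile. With *p* = 10%, 20% or 30% the plan reports the true 45th, 40th or 35th percentile as the median.

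**2. Size for full activity.** Inputs:
- Cut-off τ = 5, 6 or 7 months (Visit 7 window, Schedule of Assessments).
- N = 200 (SAP, Sample Size).
- Assumed, not in the documents: log-normal time with median *m* = 4 to 6 months and log-SD *s* = 0.25 to 0.5.

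Formulas:
- Share dated: F = Φ(ln(τ/m)/s).
- Dated-only median: m·exp(s·Φ⁻¹(F/2)).
- True mean: m·exp(s²/2).
- Dated-only mean: true mean × Φ(ln(τ/m)/s − s)/F.

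Worked case, m = 5, s = 0.4, τ = 6: ln(1.2)/0.4 = 0.456, so F = 0.676 and 32.4% (65 of 200) have no date. Φ⁻¹(0.338) = −0.418, so the dated-only median is 5·exp(−0.167) = 4.23 months. The true mean is 5·exp(0.08) = 5.42 and the dated-only mean is 4.19.

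| m | s | τ | no date (of 200) | dated-only median | too short by |
|---|---|---|---|---|---|
| 4 | 0.25 | 7 | 3 | 3.98 | 0.02 |
| 4 | 0.30 | 7 | 6 | 3.95 | 0.05 |
| 4 | 0.40 | 6 | 31 | 3.70 | 0.30 |
| 5 | 0.30 | 7 | 26 | 4.76 | 0.24 |
| 5 | 0.40 | 6 | 65 | 4.23 | 0.77 |
| 5 | 0.50 | 7 | 50 | 4.26 | 0.74 |
| 6 | 0.40 | 6 | 100 | 4.58 | 1.42 |
| 6 | 0.50 | 5 | 128 | 3.79 | 2.21 |

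The first and last rows are the extremes of the range. The sign is the same throughout.

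**3. What censoring recovers.** With 200 subjects simulated 1,000 times, log-SD 0.4 and Visit 7 uniform over 5 to 7 months:
- True median 4: Kaplan-Meier gives 3.98, dated-only gives 3.68 (about 168 dated).
- True median 5: Kaplan-Meier gives 5.00, dated-only gives 4.21 (about 134 dated).

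Censoring is independent of recovery in this simulation. If fewer than half are cleared by Visit 7, Kaplan-Meier has no median to report, so the collection period must be extended as well.

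**4. Where the cut-off does not bite at final analysis.**
- Work: collected to 24 months. With an assumed median of 2 or 3 months and log-SD 0.6, the share later than 24 months is 1 − Φ(ln(24/m)/0.6), which is 0.002% or 0.03%.
- Boot: permission is required by 3 weeks, and delays are documented and brought to an unscheduled visit (Protocol 5.3).
- Shoe: transition begins at about 6 weeks, and collection runs to Visit 7.
- Dropout unrelated to recovery (5% to 20% by 24 months, no cut-off) leaves a true 4.00-month median at 3.98 to 4.00.

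Interim analyses are different. Protocol 9.6 allows them as data become available, including for publication, using the SAP methods. A subject operated on *c* months before the data cut contributes a time only if it is at most *c*. Long times are filtered out, which shortens the shoe, work and activity summaries.

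**The case against.** **The loss is visible and not absolute.** SAP section 7 reports n and annotates tables with the population size, missing observations included. Protocol 7.10 lets an unscheduled visit collect return-to-activity data, and Protocol 5.3 sets no closing date for the full-activity date. This stands in part. The reader sees how many are missing but not that they are the slow ones. Unscheduled visits are for complications, suspected non-union or weight-bearing follow-up, so a routine late clearance need not produce one. The modelled loss is an upper case for each assumed distribution.

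**The size is assumed.** This stands. With a 4-month median, log-SD 0.25 to 0.30 and a 7-month cut, only about 1% to 3% are undated and the bias is negligible.

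**The study is descriptive.** True, and no hypothesis rests on these endpoints. A descriptive median should still describe all treated subjects.

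**Stronger readings.** A reader might infer that all five recovery endpoints are biased short at the end of the study. The documents do not support that: work dates run to Visit 9, boot permission is fixed early with a route for delays, and shoe transition lies well before Visit 7. A reader might also infer that dates of permission make recovery look faster. The documents give no lag between permission and actual start, and a date tied to a visit could be late as well as early. The different units (days in SAP 1.2.2; weeks and months in 7.2.2) are a rescaling. Dividing by 30 rather than 365.25/12 = 30.44 lengthens reported months by about 1.5%, the opposite direction.

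**Conclusion.** The concern holds for time to full unrestricted activity. Following the plan as written drops subjects cleared after Visit 7, apart from any dates recovered at unscheduled visits, and biases the median and mean short. The direction follows from the documents; the size does not. Under the stated log-normal assumptions the median is short by about 0.02 to 2.2 months: negligible if almost everyone is cleared by Visit 7, and substantial if clearance clusters around 6 months or later.

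At final analysis the cut-off has little effect on boot, shoe or work times. At any interim analysis that includes subjects still short of the milestone, the missing censoring rule would shorten the shoe, work and activity summaries. The gap between permission dates and the start or return named in the endpoints is a labelling mismatch, not a demonstrated bias. The primary endpoint is unaffected.

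**What to change.** - **SAP 6.4.1, 7.2.2 items 7 to 9, and 7.3.3:** treat a subject without a date as censored at the last assessment at which that milestone was asked, not at last contact. Report the Kaplan-Meier median and quartiles with 95% confidence intervals and the number who have not reached the milestone. Apply the same rule at interim analyses.
- **Protocol Schedule of Assessments, 7.8 and 7.9, with the matching SAP schedule:** carry the full-unrestricted-activity date question to Visits 8 and 9.
- **Endpoint names in both documents:** rename as time to clearance for boot, shoe, full activity, work and full work, so that the name matches the recorded date.
- **Units:** report in days, as in the endpoint list.

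The cost is SAP wording, one carried-forward eCRF question at two existing visits, and the corresponding schedule amendment. Reported times may become slightly longer. Kaplan-Meier adds almost nothing for boot weight-bearing, but one rule for all milestones is simpler to program and does no harm there.

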6.4.2 Change from Baseline

Change from baseline will be determined for ROM, VAS, PROMIS, MOxFAQ, and radiographic measurements (IMA, HVA, tibial sesamoid position (TSP), sagittal plane). It will be calculated as value at timepoint of interest minus value at baseline.

6.4.3 Radiographic reads

For data analysis purposes, radiographic reads will be performed by a fellowship trained musculoskeletal radiologist. The following adjustment will be made to metatarsal length measurement data prior to analysis: if metatarsal length is recorded as a positive number, it will be converted to a negative number. If metatarsal length is recorded as a negative number, it will be converted to a positive number.

6.4.4 MOxFAQ

The Manchester Oxford Foot Questionnaire (MOxFAQ)⁷ is a 16 item, subject-reported outcome measure designed for use with individuals who are undergoing foot or ankle surgery. Each of the 16 questions on the MOxFAQ is scored in the same direction with the score increasing as the reported health status becomes worse. Scores for each domain of the MOxFAQ are calculated as the sum of each individual item score. In each case, this is expressed on a metric of 0 – 100 (where a higher score represents greater severity) and will be calculated as (actual score/maximum possible domain score)*100. If a single item within any domain is unanswered, the mean value from the respondent's other item responses (series mean) within that domain will be used for the missing response. If more than one item within any domain is unanswered, then all item responses for that domain will be set to missing.

6.4.5 PROMIS-29/PROMIS-25

The PROMIS profile instruments⁶ are a collection of short forms containing a fixed number of items. The PROMIS-29 is intended for adults (aged 18+ years) and assesses seven PROMIS domains (Depression, Anxiety, Physical Function, Pain Interference, Fatigue, Sleep Disturbance, and Ability to Participate in Social Roles and Activities). The PROMIS-25 is intended for children (aged less than 18 years) and assesses six PROMIS domains (Depressive Symptoms, Anxiety, Physical Function-Mobility, Pain Interference, Fatigue, and Peer Relationships). Each domain has 4 items, with each item having five response options ranging in value from 1 to 5. A separate pain intensity item is also assessed and has eleven response options ranging in value from 0 to 10. All domains are assessed over the past seven days except for Physical Function (PROMIS-29) which has no timeframe specified.

A raw score is created from each short form that makes up the profile. To find the total raw score for a short form with all questions answered, sum the values of the response to each question within each domain. To translate the total raw score into a T-score for each short form for each participant, a PROMIS score conversion table is used. The T-score rescales the raw score into a standardized score with a mean of 50 and a standard deviation (SD) of 10. The standardized T-score is reported as the final score for each participant.

If an item in a short form is unanswered, then the total raw score and T-score for that short form will not be calculated.

6.4.6 POSAS

The Patient and Observer Scar Assessment Scale (POSAS) measures scar quality from the perspectives of both the patient and the clinician. It consists of two parts, the Patient Scale and the Observer Scale, each with 6 components that are scored on a scale of 1 – 10 where 1 indicates normal skin and 10 indicates largest difference from normal skin. Total score can range from 6 to 60 and is calculated by summing the 6 component scores.

6.4.7 Correction

Successful correction is defined as any two of the following 3 criteria being met at 6 weeks post-procedure: IMA $<9.0^\circ$, HVA $<15.0^\circ$, TSP as ≤ 3 . In other words, if none or one of the measurements is out of range at 6 weeks, the foot is considered “corrected”. If two or more measurements are out of range at 6 weeks, the foot is considered “not corrected”.

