## **3.0 STUDY ENDPOINTS**

### **Primary:**

Radiographic recurrence of hallux valgus deformity at 24 months for subjects with successful correction (defined as IMA <9.0°, HVA <15.0° and TSP as ≤ 3 at 6 weeks post-Lapiplasty® Procedure). Recurrence is defined by any two of the following three criteria being met at 24 months post-procedure: IMA of ≥12°, HVA ≥20° and TSP ≥4.

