## **9.8 Detailed Analysis Plan**

Prior to database closure, a detailed statistical analysis plan will be finalized to completely specify the statistical procedures to be applied to the data by the statistician who will conduct the analysis. The plan will amplify the methods discussed in this protocol, will address any protocol changes that would affect the analysis, and will provide a rationale for any changes to the analysis.

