6.4.8 Recurrence

Recurrence (loss of correction) is considered to have occurred at 24-months post-procedure if any two of the following 3 criteria are met: IMA of $\geq 12^\circ$, HVA $\geq 20^\circ$, TSP ≥ 4 . An alternative definition of recurrence will also be applied: HVA $\geq 15^\circ$.

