7.2.1 Primary Effectiveness Analysis

The primary effectiveness analysis will determine the proportion of subjects with radiographic recurrence of hallux valgus deformity (bunion recurrence) at 24 months, limited to subjects with successful correction at 6 weeks. Successful correction is defined as meeting 2 of the following 3 criteria: IMA $<9.0^\circ$, HVA $<15.0^\circ$ and TSP as ≤ 3 at 6 weeks post-index procedure. Recurrence is defined as meeting 2 of the following 3 criteria at 24 months post procedure: IMA of $\geq 12^\circ$, HVA $\geq 20^\circ$ and TSP ≥ 4 .

A sensitivity analysis of the primary effectiveness endpoint will be performed using the PP population if the PP and ITT populations differ considerably.

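### The SAP counts a foot as corrected on any two of three 6-week criteria where the protocol requires all three, so the primary recurrence rate has a different denominator, and no rationale is given

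*SAP*

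**What the plan says.** Protocol, synopsis and section 3.0 (Primary): the endpoint is recurrence at 24 months in subjects whose correction succeeded, and success is "defined as IMA <9.0°, HVA <15.0° and TSP as ≤ 3 at 6 weeks post-Lapiplasty® Procedure". The next sentence defines recurrence as "any two of the following three criteria being met at 24 months post-procedure: IMA of ≥12°, HVA ≥20° and TSP ≥4".

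SAP 6.4.7 uses the same three 6-week cut-offs under a different rule: "Successful correction is defined as any two of the following 3 criteria being met at 6 weeks post-procedure". It then spells out that a foot with a single measurement out of range still counts as corrected. SAP 7.2.1 repeats the rule for the primary analysis: "Successful correction is defined as meeting 2 of the following 3 criteria". SAP 1.2.1 and 7.2.1 both restrict the primary proportion to corrected subjects. The recurrence rule for the primary endpoint is the same in both documents.

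Protocol 9.8 says that the SAP "will address any protocol changes that would affect the analysis, and will provide a rationale for any changes to the analysis". The SAP text available contains no rationale for the different correction rule, and its Summary of Changes reads N/A. The only sensitivity analysis planned for the primary endpoint is on the per-protocol population, if that differs considerably from the ITT population.

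On secondary definitions, SAP 6.4.8 states: "An alternative definition of recurrence will also be applied", and gives HVA ≥15°. SAP 7.2.2 item 2 has a strict inequality: "Percentage of subjects with recurrence at 12 months and 24 months where recurrence is defined as HVA >15" degrees. Item 3 uses HVA >20°, against ≥20° in the composite definition.

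**The concern.** The 6-week rule decides who is at risk in the primary endpoint. If the protocol and SAP define it differently, they estimate recurrence in different sets of feet, and an analyst who follows the SAP will not report the protocol's primary endpoint at all.

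The difference also affects what the rate means. Under the protocol, every foot at risk starts clear of all three recurrence criteria, so a recurrence needs two measurements to move from in range to beyond the recurrence cut-off. Under the SAP, a foot may start with one measurement already beyond that cut-off, and one further change makes it a recurrence. SAP 6.4.8 equates recurrence with loss of correction, but part of what is counted could be deformity that was still present at 6 weeks.

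The same definition feeds SAP 7.2.2 item 4, the percentage of subjects corrected at 6 weeks. That percentage can only stay the same or rise under the looser rule.

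**Working it through.** The plan has no figure to reproduce: the sample of 200 was chosen for feasibility, and no correction or recurrence rate is assumed. The check is therefore an enumeration, followed by an illustration on stated assumptions.

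**1. Patterns admitted.** Each criterion is met or not met at 6 weeks, giving 2³ = 8 patterns. The protocol admits 1 (all met). The SAP admits 4 (all met, or exactly one failed).

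**2. Where the added feet stand on recurrence.** Split IMA into <9°, 9 to <12° and ≥12°; HVA into <15°, 15 to <20° and ≥20°; and TSP into ≤3 and ≥4. The TSP split assumes whole-number grades, which leave no gap between the two cut-offs. That gives 3 × 3 × 2 = 18 states, of which the protocol admits 1 and the SAP 6:

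| IMA | HVA | TSP | Protocol | SAP | Recurrence criteria already met at 6 weeks |
|---|---|---|---|---|---|
| <9° | <15° | ≤3 | yes | yes | 0 |
| 9 to <12° | <15° | ≤3 | no | yes | 0 |
| ≥12° | <15° | ≤3 | no | yes | 1 |
| <9° | 15 to <20° | ≤3 | no | yes | 0 |
| <9° | ≥20° | ≤3 | no | yes | 1 |
| <9° | <15° | ≥4 | no | yes | 1 |

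Of the 5 added states, 3 already meet one of the two criteria needed and 2 meet none. No admitted state meets two. A foot that fails on TSP alone is always one criterion short of recurrence. A foot that fails on IMA or HVA alone is so only at ≥12° or ≥20°.

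**3. Size of the denominator gap (illustration).** Assume 200 evaluable feet and the same probability p of meeting each criterion, independently. Then P(all three) = p³ and P(at least two) = p³ + 3p²(1−p).

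| p (assumed) | Protocol, 200 × p³ | SAP, 200 × [p³ + 3p²(1−p)] | Added feet |
|---|---|---|---|
| 0.80 | 102.4 | 179.2 | 76.8 |
| 0.90 | 145.8 | 194.4 | 48.6 |
| 0.95 | 171.5 | 198.6 | 27.1 |
| 0.98 | 188.2 | 199.8 | 11.5 |

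Three measurements on one foot are unlikely to be independent, and positive correlation narrows the gap. With a Gaussian copula at correlation 0.6, the added feet number about 39, 26 and 16 at p = 0.80, 0.90 and 0.95. At correlation 0.8 and p = 0.95 they number about 10.

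**4. Direction of the effect on the rate (illustration).** Let r₁ be the recurrence risk in fully corrected feet and r₂ the risk in the added feet. The SAP rate is a weighted mean of the two. At p = 0.90 with independence, the weights are 0.729/0.972 = 0.75 and 0.243/0.972 = 0.25. Take r₁ = 3.3%, the complement of the 96.7% who kept their correction in the retrospective study cited in protocol 1.0, used here only as a placeholder:

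- r₂ = 0: 0.75 × 3.3% = 2.5%
- r₂ = 3.3%: 3.3%
- r₂ = 10%: 2.475% + 2.5% = 5.0%
- r₂ = 20%: 2.475% + 5.0% = 7.5%

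The protocol rate is 3.3% in every case. The SAP rate is lower, equal or higher according to r₂, which the documents do not give.

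**The case against.** The strongest reply is that the study is single-arm and mainly descriptive, with no success threshold and no formal sample size, so no test decision turns on the denominator. That stands: the harm is to consistency and interpretation. It does not remove the contradiction, because the descriptive rate is the study's primary result.

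A second reply is that the protocol sentence is a plain list and could have been meant as two of three. The text does not support this. The protocol writes the any-two wording in the very next sentence, for recurrence only.

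A third is that the N/A in the SAP's Summary of Changes may refer only to changes between SAP versions. That is possible, but the rationale called for by protocol 9.8 does not appear elsewhere in the SAP text either.

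Three stronger readings are tempting and should not be drawn:

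- A reader might infer that every added foot is half-way to recurrence. Feet with IMA 9 to <12° or HVA 15 to <20° meet no recurrence criterion.
- A reader might infer that the larger denominator flatters the result, by dividing the same number of recurrences by more feet. That supposes no recurrences among the added feet. If they recur more often than fully corrected feet, the SAP rate is higher.
- A reader might infer that the rule was chosen after data were seen, since the study is unblinded and allows interim analyses. The documents do not date the SAP rule relative to any data, and protocol 9.6 only permits publication of interim results. An unreconciled difference between document versions would explain the text equally well.

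**Conclusion.** The contradiction stands and must be resolved before the primary analysis. Protocol 3.0 requires all three 6-week criteria; SAP 6.4.7 and 7.2.1 require two. The primary denominators therefore differ, no reason is given, and no planned output uses the protocol's rule. The SAP set also includes some feet that already meet one recurrence criterion at 6 weeks (TSP ≥4 alone, HVA ≥20° alone or IMA ≥12° alone), so residual deformity can be mixed with recurrence.

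The definitional finding rests on the wording alone; the statement that every TSP-only failure is at ≥4 also assumes whole-number grades. The size does not follow from the documents. The 146 against 194 feet is an illustration that assumes 200 evaluable feet, 90% success on each criterion and independence. Enrolment is only up to 200, and missing values are not imputed. Correlation or higher success rates shrink the gap, to about 10 feet in the narrowest case quoted above. The direction of the effect on the rate is undetermined.

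The HVA wording is a minor matter. The ≥15° and >15° forms differ only for a foot measuring exactly 15°. The HVA >20° rate is a separate single-criterion definition, so it does not contradict the composite's ≥20°, but one form would be cleaner. SAP 7.2.2 items 2 and 3 do not state their denominators. That is an omission and should not be read as a decision to include uncorrected feet.

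**What to change.** In SAP 6.4.7 and 7.2.1, define successful correction for the primary analysis as in the protocol: IMA <9.0°, HVA <15.0° and TSP ≤3, all at 6 weeks. The definition then carries through to 7.2.2 item 4. Report the two-of-three rule as a labelled sensitivity analysis, with its own denominator, and record the change in the SAP.

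If the sponsor prefers two-of-three as the primary rule, the alternative is to amend the protocol, give the rationale, record it in the SAP and report both denominators.

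Minor edits at the same time: use one inequality for the alternative recurrence threshold (6.4.8 against 7.2.2 item 2), use one form for HVA 20°, and state the denominator for each HVA-only rate.

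The first route costs SAP wording, one extra table row or footnote, and a primary denominator that is smaller whenever any foot fails exactly one criterion. The second costs a protocol amendment. Neither needs new data.
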